9.4 Recommendation on glucose monitoring with copanlisib

Glucose monitoring for the first copanlisib administration

- Blood glucose will be measured at 0h (predose) and ~1 h after completion of infusion and subsequently if clinically indicated, at the discretion of the investigator. Patients should be educated on the signs and symptoms of hyperglycemia, such as frequent urination, increased thirst, blurred vision, headaches, and difficulty concentrating, and must report these to the investigator or their physician immediately.

Glucose monitoring for the second copanlisib infusion

- If hyperglycemia is <250 mg/dl after the first copanlisib infusion, at the discretion of the investigator, post-infusion glucose monitoring may or may not be performed. Pre-infusion glucose testing before copanlisib is required to ensure fasting levels <160 mg/dl or random/nonfasting glucose levels <200 mg/dl.

Glucose monitoring at home

- For all patients who experience persistent glucose >250 mg/dl (13.9 mmol/L) or who receive antidiabetic treatment on the day of infusion, fasting glucose should be measured the next day. If the glucose reading is <100 mg/dl (5.5 mmol/L; nondiabetic) or <160 mg/dl (8.9 mmol/L; diabetic), record the reading and stop further glucose measurements until the next copanlisib infusion. If the glucose reading is >100 mg/dl (5.5 mmol/L; nondiabetic) or >160 mg/dl (8.9 mmol/L; diabetic), inform the study nurse or investigator. If the patient has known diabetes and already monitors his/her blood glucose as part of routine diabetes care, the routine measurements should not be replaced by the study-specific measurements. In this situation, patients should add the study-specific measurements to their routine.

- For patients without diabetes who experience persisting glucose >250 mg/dl (13.9 mmol/L) or who require treatment to maintain optimal glucose levels, consultation with an endocrinologist is encouraged. These patients without diabetes will be trained on how to measure their capillary blood glucose levels at home. If applicable, patients will be provided with a glucose meter and supplies (e.g., lancets, test strips, and diary) to register measured values and record oral glucose-lowering medication and/or insulin administration.

Please refer to **Table 11-13** and consider consultation with an endocrinologist for the management of hyperglycemia.

9.5 Concomitant medications and therapies

Permitted concomitant therapy:

- Standard therapies for concurrent medical conditions
- Treatment with nonconventional therapies (for example, herbs or acupuncture) and vitamin/mineral supplements is acceptable, provided they do not interfere with the study endpoints, in the opinion of the Investigator. St. John's wort is not permitted.
- Bisphosphonates or other bone-modifying agents (e.g., denosumab)
- Patients who are therapeutically treated with an agent such as warfarin or heparin will be allowed to participate, provided their medication dose and international normalized ratio/partial thromboplastin time is stable. Close monitoring is recommended, in accordance with the standard of care. If either of these values is above the therapeutic range, the doses should be modified and the assessments should be repeated weekly until the value(s) become(s) stable.
- Antiemetics: prophylactic anti-emetics may be administered in accordance with standard practice. The routine use of standard antiemetics, including 5-HT3 blockers, such as granisetron, ondansetron, or an equivalent agent, is allowed as needed.
- The use of corticosteroids as antiemetics before copanlisib administration will not be allowed (given the risk of worsened hyperglycemia).
- Palliative and supportive care for the other disease-related symptoms and for toxicities associated with treatment will be offered to all patients in this trial.
- Patients may receive palliative and supportive care for any underlying illness.
- Low-dose aspirin (maximum 100 mg/day) and low-dose heparin are permitted.
- Patients taking narrow-therapeutic-index medications should be monitored proactively if these medications cannot be avoided. These medications may include quinidine, cyclosporine, and digoxin.
- Therapeutic drugs known to be substrates of P-gp and/or BCRP with narrow therapeutic index should be used with caution, and patients should be monitored for any sign of toxicity. Furthermore, sensitive substrates of the renal drug transporter MATE2K (e.g., metformin) should be used with caution (see **Appendix E**). Metformin should be interrupted for 48 h after receipt of iodinated contrast media. Please see prescribing information for further information.
- Calcium channel blockers may be used to control preexisting hypertension. Nondihydropyridine calcium channel blockers (e.g., verapamil and diltiazem) should be avoided because of a potential interaction with CYP3A4.
- Short-term (up to 7 days) systemic corticosteroids >15 mg prednisone or equivalent will be allowed for the management of acute conditions (e.g., treatment of noninfectious pneumonitis [NIP]).

Prohibited concomitant therapy:

The following medications are prohibited during study treatment (see **Table 9-2** below).

This list is not comprehensive and is only meant to be used as a guide.

- Strong inhibitors or inducers of CYP3M/5
- Substrates of CYP3A4/5 with narrow therapeutic index
- Medications that carry a strong risk for QT prolongation
- Herbal medications/preparations (except for vitamins)
- Other investigational and antineoplastic therapies
- Anti-arrhythmic therapy other than beta blockers or digoxin
- Systemic corticosteroid therapy at a daily dose >15 mg prednisone or equivalent. Previous corticosteroid therapy must be stopped or reduced to the allowed dose at least 7 days before study registration. If a patient is on chronic corticosteroid therapy, corticosteroids should be de-escalated to the maximum allowed dose before the screening. Patients may be using topical or inhaled corticosteroids. Short-term (up to 7 days) systemic corticosteroids >15 mg prednisolone or equivalent will be allowed for the management of acute issues. The use of corticosteroids as antiemetics before copanlisib administration will not be allowed.
- Ongoing immunosuppressive therapy
- Concomitant radiotherapy
- Herbal medications, including but not limited to St. John's wort, Kava, ephedra (ma huang), ginkgo biloba, dehydroepiandrosterone (DHEA), yohimbe, saw palmetto, black cohosh, and ginseng. Patients should stop using all herbal medications at least 7 days before the first dose of study treatment.

Table 9-2: List of prohibited medications during the study

Category	Drug name
Strong CYP3A inhibitors	Voriconazole, boceprevir, clarithromycin, cobicistat, conivaptan, danoprevir/ritonavir, eltegravir/ritonavir, grapefruit juice, indinavir/ritonavir, itraconazole, ketoconazole, lopinavir/ritonavir, mibefradil, nefazodone, neflifavir, posaconazole, ritonavir, saquinavir, saquinavir/ritonavir, telaprevir, telithromycin, tipranavir/ritonavir, troleandomycin
Moderate CYP3A inhibitors	Grapefruit, grapefruit hybrids, pum melos, star-fruit, Seville oranges (citrus paradisi fruit juice)
Strong CYP3A inducers	Avasimibe, carbamazepine, mitotane, phenobarbital, phenytoin, rifabutin, rifampin (rifampicin), St. John's wort (hypericum perforatum)
CYP3A substrates with narrow therapeutic index (NTI)	Alfentanil, apixaban (doses >2.5 mg only), aprepitant, astemizole, cisapride, cyclosporine, diergotamine, dihydroergotamine, ergotamine, fentanyl, lovastatin, nicardipine, nisoldipine, pimozide, quinidine, rivaroxaban, simvastatin, sirolimus, tacrolimus, terfenadine, thioridazine

Other investigational and antineoplastic therapies	Other investigational therapies must not be used while the patient is on the study. Anticancer therapy (chemotherapy, biologic or radiation therapy, and surgery) other than the study treatments must not be given to patients while the patient is on the study medication. If such agents are required for a patient, the patient must discontinue the study.
Herbal preparations/medications	Herbal preparations/medications are prohibited throughout the study. These herbal medications include but are not limited to St. John's wort, Kava, ephedra (ma huang), ginkgo biloba, dehydroepiandrosterone (DHEA), yohimbe, saw palmetto, and ginseng. Patients should stop using these herbal medications 7 days before the first dose of study medication.

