6.2 Subject Exclusion Criteria

- Untreated metastatic brain or leptomeningeal tumors (metastatic brain or leptomeningeal tumors treated with radiation and/or surgery are allowed)
- Prior malignancy if diagnosed and treated within 2 years of trial drug initiation (with the exception of nonmelanoma skin cancers or Stage I cancers treated with curative intent). Patients may be included if they have completed therapy for a prior malignancy >2 years before drug initiation and currently have no evidence of disease
- Inability to follow a low-iodine diet or requiring a medication with a high content of iodide (amiodarone)
- Current congestive heart failure class >2 , as defined by the New York Heart Association functional classification system
- Myocardial infarction <6 months before the initiation of protocol
- Unstable angina (angina symptoms at rest) or new-onset angina (begun within the last 3 months)
- Uncontrolled hypertension (blood pressure $>150/90$, despite optimal medical management)
- Uncontrolled type I or II diabetes mellitus, as judged by the investigator, or Hgb A1C of >8.5
- Arterial or venous thrombotic event or embolic event, such as a cerebrovascular accident (including transient ischemic attacks), deep vein thrombosis, or pulmonary embolism, within 3 months before the start of study medication
- Nonhealing wound, ulcer, or bone fracture (tumor-related nonhealing wounds are allowed)
- Active, clinically serious infections CTCAE v5.0 grade >2
- History of concurrent condition of interstitial lung disease and/or severely impaired lung function

- Known history of HIV infection (all patients must be screened for HIV up to 28 days before start of study)
- Seizure disorder requiring medication
- Therapy with a prohibited concomitant medication (**Section 9.5**) that cannot be temporarily held (at least 2 weeks before initiation of vemurafenib plus copanlisib until 1 week after the last dose) or replaced with a nonprohibited concomitant medication
- Systemic corticosteroid therapy at a daily dose >15 mg prednisone or equivalent (previous corticosteroid therapy must be stopped or reduced to the allowed dose at least 7 days before study registration)
- Cytomegalovirus (CfV1V) PCR-positive at baseline
- Evidence or history of a bleeding diathesis or any hemorrhage or bleeding CTCAE v5.0 grade 3 within 4 weeks before the start of study protocol

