Blood pressure will be measured every 5-10 min before each copanlisib dose (no more than 4 measurements) until 2 consecutive results <150/90 mmHg are recorded. If blood pressure is 150/90 mmHg, the investigator can consider a medical intervention or delay infusion of the study drug. The patient should rest for 5-10 min before blood pressure is recorded.

On infusion days, blood pressure will be measured at 0h (predose), 30 min (midinfusion), 60 min (end of infusion), and 1 h after the end of infusion.

Note: A window of ± 10 min is allowed for all blood pressure measurements, except for the 0-h (predose) measurement.

No dose should be given if blood pressure is 150/90 mmHg. Antihypertensive medication may be given to control increased blood pressure. Dosing can proceed on the scheduled day if at least 2 consecutive measurements <150/90 mmHg are recorded. Otherwise, dosing must be delayed.

If drug-related arterial hypertension (postdose blood pressure of CTCAE grade 3 or 160/100 mmHg) is not manageable with optimal antihypertensive treatment, the dose for the subsequent copanlisib administrations should be at the next lowest dose level. Patients with a postdose blood pressure that may have life-threatening consequences (e.g., malignant arterial hypertension, transient or permanent neurologic deficit, hypertensive crisis) must permanently discontinue the study drug.

It is important that patients with preexisting arterial hypertension adhere to their regular medication schedule and take their usual doses on the days of study drug infusion.

The management of acute blood pressure increases following copanlisib will be individualized for each patient, but the experience in phase I study has suggested a benefit of dihydropyridine calcium channel blockers (i.e., amlodipine, felodipine). Nitrates should also be considered. Verapamil and diltiazem (non-dihydropyridine calcium channel blockers and moderate inhibitors of CYP3M) should be used with caution, owing to a potential interaction with CYP3M. In general, it is advisable for sites to be prepared so that antihypertensive medication is readily available if needed.

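### Section 9.5 both permits and prohibits quinidine, cyclosporine and herbal products; for the two drugs this gives opposite eligibility decisions

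*Combined protocol and SAP*

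**What the plan says.** **Permitted list, Section 9.5.** Narrow-therapeutic-index drugs come with an instruction to monitor proactively where they are unavoidable. The examples follow: "These medications may include quinidine, cyclosporine, and digoxin". On herbs, the entry begins "Treatment with nonconventional therapies (for example, herbs or acupuncture" and goes on to accept these, with vitamin and mineral supplements, if the investigator judges that the endpoints are not affected. St. John's wort is the only stated exception.

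**Prohibited list, Section 9.5.** It bans narrow-index substrates of CYP3A4/5 as a class. It also bans "Anti-arrhythmic therapy other than beta blockers or digoxin" and continuing immunosuppression. Herbal preparations appear twice: once as a class with vitamins exempt, and once with named examples and an instruction to stop all of them 7 days or more before dosing.

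**Table 9-2.** The row for narrow-index CYP3A substrates names cyclosporine and, further along, "nisoldipine, pimozide, quinidine, rivaroxaban, simvastatin, sirolimus, tacrolimus". The herbal row states: "Herbal preparations/medications are prohibited throughout the study".

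**Section 6.2.** One exclusion criterion is "Therapy with a prohibited concomitant medication", with a pointer to Section 9.5. It applies where the drug can be neither held for a defined interval nor replaced by one that is not prohibited.

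**Verapamil and diltiazem.** In Section 9.5, under control of preexisting hypertension, they "should be avoided because of a potential interaction with CYP3A4". In Section 11.2, in the hypertension recommendations on acute rises after copanlisib, they "should be used with caution, owing to a potential interaction with" the same enzyme family.

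**The concern.** A co-medication rule that is also an exclusion criterion has to give one answer per product. Under Section 15.1, the person who signs the Eligibility Checklist confirms whether or not the patient qualifies. For a patient who cannot come off quinidine or cyclosporine, that person finds one line in Section 9.5 that allows the drug with monitoring and another that, through Section 6.2, keeps the patient out. Two staff members could each follow the protocol and decide in opposite ways. The same holds for a patient who wishes to take a herbal product during study treatment, although there the disagreement is about what may be taken and not about who may enter.

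**Working it through.** No arithmetic applies, and the plan states no figure on this point. The check is to set the rules side by side.

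| Product | Permitted list (9.5) | Prohibited list (9.5) | Table 9-2 | Section 6.2 consequence |
|---|---|---|---|---|
| Quinidine | Named; monitor if unavoidable | Caught as a narrow-index CYP3A4/5 substrate | Named | Excluded if it cannot be held or replaced |
| Cyclosporine | Named; monitor if unavoidable | Caught as a narrow-index CYP3A4/5 substrate | Named | Excluded if it cannot be held or replaced |
| Herbs other than St. John's wort | Acceptable at the investigator's judgement | Banned, in two entries | Banned throughout | Can be stopped, so entry is unlikely to turn on it |
| Verapamil, diltiazem | Avoid (preexisting hypertension) | Not named | Not named | No direct link |

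1. **Quinidine and cyclosporine.** Both are named in the permitted list and in Table 9-2, so the usual rule that a specific entry overrides a general one cannot settle it. The conditions also coincide. The permitted sentence applies when the drug is unavoidable; the exclusion applies when it can be neither held nor replaced. In practice these describe the same patient, who gets opposite answers. The bans on other anti-arrhythmics and on immunosuppression point the same way as Table 9-2 if the two drugs are classed in the ordinary manner, but the contradiction does not need that step.

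2. **Digoxin.** It appears in the same permitted sentence but is not in conflict, because the anti-arrhythmic ban exempts it.

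3. **Herbs.** One permissive sentence stands against three prohibitions: two in the list and one in Table 9-2. Because the documents treat herbs as something patients stop before dosing, the conflict bears on co-medication during the study.

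4. **Verapamil and diltiazem.** Both places discourage use and give the same reason. They differ in strength (avoid against caution) and in setting (preexisting hypertension against acute rises after infusion). Section 11.2 calls the two drugs moderate CYP3A inhibitors. The prohibited list covers strong inhibitors, and the moderate-inhibitor row of Table 9-2 holds only fruit and juice items. They therefore do not clearly trigger Section 6.2.

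5. **Related loose ends.** Section 9.5 has herbs stopped 7 days or more before dosing, while Section 6.2 defines the hold for a prohibited medication as 2 weeks or more before the combination starts. Appendix E lists sirolimus, posaconazole and lovastatin for cautious use, while Table 9-2 prohibits them. Both suggest that the lists were not checked against one another.

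**The case against.** The best defence is that a careful reader would settle most of this on the side of prohibition. Each disputed product is barred in more than one place against a single permissive sentence, and the sentence on drugs itself presumes that they are avoided where possible. Section 9.5 also describes its prohibited list as incomplete and meant as guidance.

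Part of this stands: the day-to-day ambiguity is smaller than a bare list of conflicts suggests. It does not remove the contradiction. The guidance remark leaves room for drugs that are not listed; it does not reconcile drugs named on both sides. Section 6.2 also gives the list the force of an exclusion criterion. Counting mentions is not a rule that the protocol gives its staff.

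A reader might go further and infer that the conflict threatens the dose-escalation result, since CYP3A interactions can alter exposure and the cohorts hold 3 to 6 patients. The documents do not support that for the products in real conflict:

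- Table 9-2 classes quinidine and cyclosporine as CYP3A substrates, not inhibitors or inducers. On that classification the worry is the level of the co-medication, not of vemurafenib or copanlisib.
- No CYP3A reason is given for herbs as a class. St. John's wort is the only herb in the inducer row, and both lists bar it.
- Section 9.2 counts a toxicity as dose-limiting only if it is attributed to one or both study drugs.
- One such event among the first 3 patients adds 3 more at that level, and escalation still follows if no further event occurs. It changes the next step, not necessarily the outcome.

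**Conclusion.** The contradiction is real and lies in legible, operative text; it does not depend on a lost symbol or a redaction. For quinidine and cyclosporine it produces opposite eligibility decisions. For herbal products it produces opposite co-medication decisions during the study. The verapamil/diltiazem difference is a minor mismatch of wording across two settings. A reader might infer that all five items govern entry, but only the two drugs do so on the text.

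The size is small. The documents do not say how many patients take any of these products, and I assume few among the planned 6 to 32. Sample size and error rates are unaffected, and no bias in the toxicity counts is shown for quinidine, cyclosporine or herbs as a class. This is an internal inconsistency worth correcting, not a flaw in the design. I take no view on which status is clinically right.

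**What to change.** Reconcile the permitted list, the prohibited list and Table 9-2 so that quinidine, cyclosporine and herbal products each have a single status. Make sure that the Section 6.2 exclusion and the Eligibility Checklist apply that status. Align the verapamil/diltiazem wording in Section 9.5 and in the hypertension recommendations of Section 11.2, or say explicitly that the two settings are meant to differ. The clinical team must choose each status.

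The same pass should reconcile the herbal stopping interval with the hold interval in Section 6.2, and Appendix E with Table 9-2.

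The cost is text editing: Section 9.5 with its table, one sentence in Section 11.2, and a cross-check of Section 6.2 and Appendix E. Nothing changes in the sample size, the escalation rules or the analysis.

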9.6 Correlative studies

Exploratory objective: To evaluate how vemurafenib and copanlisib affect MAPK/PI3K signaling and thyroid differentiation in tumors of patients with RAI disease. Biopsies will be performed at baseline and on treatment with vemurafenib plus copanlisib (as in **Table 10-2**), unless the patient is exempt (**Section 6.1**). Biopsies of any tumor site is allowed, but metastatic tumors are preferred, and every attempt should be made when performing both biopsies to obtain tissue from the same tumor. The RNA and DNA assays suggested below may be substituted for other techniques or platforms, depending on availability.

Transcriptomic and protein-based analyses of serial biopsy specimens: As the amount of frozen tissue obtained from biopsies is limited, we will prioritize sensitive array-based technologies to quantify gene expression and to sequence cancer genes. We will isolate RNA from pre- and post-treatment biopsy specimens for interrogation. RNAseq will be performed to quantify transcripts regulated by MAPK (MAPK output),²² the BRAF-RAS score (a 71-gene signature that distinguishes BRAF^{V600E} from RAS mutant tumors⁵), and the enhanced Thyroid Differentiation Score (which is a gene signature of thyroid-specific differentiation.⁵ Each of these scores provides an average fold-change for all mRNAs in the respective gene sets, compared with the median of all samples. In addition, we will measure the effects of vemurafenib plus copanlisib on the transcription of iodine organification genes and PI3K transcriptional output. These transcriptomic readouts will then be analyzed in the context of change in lesional 1-124 concentration observed with 1-124 PET. The transcriptomic data will also be investigated for other exploratory pathways, signatures, and biologic parameters. Alternative platforms to RNAseq may also be used if appropriate and available. Other protein markers of interest, such as phospho-AKT, may be analyzed by the appropriate assay (e.g., immunohistochemistry, Western blot, mass spectrometry, reverse protein phase array).

Genomic Analysis: Baseline genomic analysis will be performed using MSK-IMPACT, a next-generation sequencing platform.²³ Alternative techniques may be considered or performed (e.g. Sequenom analysis, Sanger sequencing, whole-exome) at the time of analyses, if deemed appropriate.

